##### **3.3.12.2.2 Method**

Tolerability. Adverse events will be tabulated. The primary safety measures will be changes in vital signs, psychological or other clinically significant adverse events, and serious adverse events using the FDA definition. Blood pressure and ratings will be contrasted by group using t-tests. AEs will be MedRA coded and groups contrasted using Chi squared or Fisher's exact test. All tests will be unprotected against inflated Type I error thus providing the most liberal estimate for potential safety concerns.

Psychoactivity. Scores from the HRS and other scales (mean, SD, median, range) will be computed and reported. Scores will be contrasted by group using t-tests for independent samples. Mean scores will be compared descriptively to means reported in other studies, particularly Griffiths et al. [97, 110].

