### 3.3.5 Randomization and Blinding

Randomization will be performed as close as possible to the first drug administration session (on the morning of the session if possible) in order to restrict the intent-to-treat sample to patients who actually receive study medication. The randomization will be stratified by site and will consist of balanced varied size blocks within strata to ensure relative equality of assignment across treatment groups. The block sizes will not be revealed to participating investigators and will be randomly selected from a small number of different block sizes to help reduce the likelihood of an investigator predicting the next treatment assignment. The study statistician will generate the randomization scheme for each site, and the study pharmacist will assign treatment sequentially according the sequence for each site.

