Participants with elevated blood pressure on screening (i.e., reading above 140/90 mmHg but no higher than 165/95 mmHg) who otherwise qualify for the study may be provisionally included and referred to their primary care provider for management of hypertension. For all participants, vital signs will be measured at all assessment visits, and may be monitored at therapy visits at the discretion of the study physician.

Participants will receive study medication only if blood pressure is less than or equal to 140 systolic, 90 diastolic at safety screening on the day of the drug administration sessions. Participants with a blood pressure reading greater than 165/95 at screening will be excluded from the study.

Participants with a BMI exceeding 35 at screening who otherwise qualify for the study will be administered a dose of study medication that corresponds to the body weight that would yield a BMI of 35 for their height.

\*Acceptable methods of contraception include oral contraceptives, barrier with spermicide, IUD, levonorgestrel implant (Norplant), medroxyprogesterone acetate (Depo provera), surgical sterilization, contraceptive patch, vaginal contraceptive ring, and complete abstinence (not having sex).

\*Significantly impaired liver function is defined as 1) Alanine aminotransferase (ALT) and/or aspartate aminotransferase (AST)  $> 5 \times$  upper limit of normal (ULN); 2) ALT or AST  $> 3 \times$  ULN with concomitant total bilirubin  $> 2.0 \times$  ULN; or 3) ALT or AST  $\geq 3 \times$  ULN with the appearance of fatigue, nausea, vomiting, right upper quadrant pain or tenderness, fever, rash, and/or eosinophilia.

^Severe asthma is defined as asthma diagnosis along with any of the following: 1) an active or chronic cough, 2) current respiratory infection 3) current difficulty breathing 4) asthma-related emergency room visit, hospitalization, or oral, intravenous, or intramuscular steroidal treatment within the past 6 months. Participants with asthma diagnosis that are included in the study and are currently using an inhaler will be asked to bring their inhaler to the medication sessions.

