##### ***3.3.8.1.3 Dosing and Administration of Study Medications***

Setting. The psilocybin sessions will take place in outpatient facilities that are appropriate for hallucinogen administration sessions. To the extent possible, the room used for the session will be specially prepared for the sessions to provide a warm and home-like rather than a stark clinical quality because of the large influence that setting can have on the subjective effects of hallucinogens. Each site will have detailed SOPs in place for managing medical or psychiatric emergencies should any occur.

Safety Screening on the Day of Drug Administration Sessions. Participants will be required to attempt to remain abstinent during the week preceding the drug administration sessions. On the morning of the psilocybin session, participants must have a negative breathalyzer reading, drug screen must be negative for all non-prescribed tested drugs of abuse except for marijuana, CIWA-Ar score must be less than 8, and vital signs must be within normal limits (afebrile, blood pressure less than or equal to 140 systolic, 90 diastolic, resting pulse less than 100). Female participants of childbearing potential must also have a negative urine pregnancy test.

Dosing of Study Medications. Individualized doses of psilocybin will be prepared by the site pharmacist using an analytical balance. Medication will be placed in an opaque gelatin capsule prior to administration, with the balance of the capsule volume filled with microcrystalline cellulose.

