Monitoring and Safety Procedures. As psilocybin use is associated with a small risk of emesis, participants will be instructed to have only a light breakfast on the morning of the psilocybin administration sessions, at least an hour before the beginning of the session. Participants will complete assessments including confirmation of medical stability and drug- and alcohol-free status. (If the participant has CIWA-Ar score of 7 or greater, need for detoxification will be assessed and the patient will be referred for treatment if indicated). They will then ingest the capsule containing the study medication, followed by approximately 4 ounces of water. Participants will remain under observation for at least 8 hours following psilocybin administration (maximal effects are expected to occur at approximately 2-3 hours). Two therapists will be present throughout all psilocybin administration sessions (except for breaks, which will be taken one at a time). Interaction with the participants will be supportive and non-directive. Vital signs will be monitored by study staff at 30 minute intervals for three hours, and then hourly. At the time of vital sign measurement, the therapists will also check in with briefly with participants and complete a brief Monitor Rating Questionnaire. Management of hypertension will be as follows. If BP is greater than or equal to 180 systolic or 100 diastolic, subjects will be assessed for discomfort that may be causing the BP elevation, e.g. anxiety, headache/pain, or alcohol withdrawal. These symptoms should be addressed/medicated, and BP will be reassessed at 15 minute intervals until below 180/100. If patient has >2 BP readings of 200/110 or higher, then the BP will be treated directly. At this time, the patient should specifically be assessed for new chest pain, shortness of breath, or focal weakness, in which case the subject will need more urgent medical attention. The following medications will be available for administration by the study physician if needed to treat hypertension (captopril 25 mg orally/sublingually, clonidine 0.1 mg orally, or hydralazine 10 mg orally). In the event that a subject experiences distressing anxious or psychotic symptoms during the experimental or control session, the clinical personnel in attendance will initiate verbal communication designed to reorient and reassure the subject. If that does not effectively alleviate the signs of an anxious or psychotic reaction, diazepam 5-10 mg, orally, or lorazepam 1 mg, intramuscularly, will be administered to lower anxiety. Only if that is ineffective or if the participant presents a danger to self or others will an antipsychotic be administered, olanzapine 5-10 mg, given either orally or intramuscularly. For headache or pain, Tylenol 500-1000 mg and/or Ibuprofen 600 mg-800 mg may be administered once orally.

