#### **3.3.12.2 Aim 1 (to characterize the acute effects of PO psilocybin 25 mg/70kg, 30mg/70kg, and 40 mg/kg in alcohol dependent patients)**

##### **3.3.12.2.1 Outcome measures**

The primary safety measures will be changes in vital signs, psychological or other clinically significant adverse events, and serious adverse events using the FDA definition. The primary measure of hallucinogen effect is the 5-Dimensional Altered States of Consciousness Scale (5D-ASC) [130]. Secondary outcomes the Intensity score and other subscales from the Hallucinogen Rating Scale (HRS) [157], the Mysticism scale [132], the Mystical Experience Questionnaire [97], abuse potential visual analog scales, and within-session Monitor Rating Scale Scores.

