#### **3.3.12.7 Statistical power**

Power analysis is based on the primary outcome analysis contrasting the psilocybin group with the control group with respect to percent heavy drinking days in months 1-8 post pharmacologic treatment (Aim 2). With a total sample size of  $n = 180$  (90 assigned to psilocybin and 90 to control), and 5% attrition (realistic because useable data require only 1 month follow-up in participants who have already participated for 1 month,  $N = 171$ ) our power analysis was based on the assumption that four predictors would be in the regression-based HLM model. We estimate that the study has power of 0.8 to detect an effect of size  $f^2 = .065$ , with alpha = 0.05 (2-tailed) and no correction for multiple comparisons. This effect is comparable to that of naltrexone [9, 158, 159], and smaller than those observed in some recent trials of other promising medications [160-162]. Regardless of the statistical significance of these changes, standardized and non-standardized effect sizes will be computed for primary and secondary outcome variables. The addition of an open-label optional third dosing does not affect the required sample size for Aim 2 (primary outcome), but approximately doubles the sample size for Aim 1 and allows for the addition of Aim 5.

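### Free improvement: the Aim 1 blood pressure comparison would be somewhat more precise if it adjusted for the pre-dose reading that every dosed participant already has

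*Combined protocol and SAP*

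**What the plan says.** Section 3.3.12.2.1 lists the Aim 1 safety outcomes: "The primary safety measures will be changes in vital signs", together with adverse events. The method in section 3.3.12.2.2 is "Blood pressure and ratings will be contrasted by group using t-tests", with no correction for multiplicity. No covariate, interval or precision target is given for blood pressure, and neither the in-session reading to be analysed nor the reference value for change is defined.

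A pre-dose value exists for everyone who is dosed. Section 3.3.6.2: "Participants will receive study medication only if blood pressure is less than or equal to 140 systolic, 90 diastolic at safety screening". Section 3.3.8.1.3 repeats the condition for the session morning and adds pulse: "blood pressure less than or equal to 140 systolic, 90 diastolic, resting pulse less than 100". In-session readings are repeated: "Vital signs will be monitored by study staff at 30 minute intervals for three hours, and then hourly". Sections 3.3.10.1 and 3.3.10.9 give half-hourly readings for two hours instead of three.

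On timing, section 3.3.5 has "Randomization will be performed as close as possible to the first drug administration session (on the morning of the session if possible". Elsewhere the plan does adjust for baseline: the primary drinking model (3.3.12.3.2) carries drinking in weeks 1-4 as a covariate, and the mediation models (3.3.12.4.2) enter baseline values. Section 3.3.12 refers the reader to a separate SAP for the full description; that text is not in the supplied material.

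**The concern.** A t-test on in-session pressure makes no use of the pre-dose reading and leaves any chance imbalance in it within the comparison. A t-test on change uses the reading, but with its coefficient fixed at 1, which over-corrects whenever the true slope is below 1. Analysis of covariance estimates the slope. Apart from one degree of freedom, it is at least as precise as either.

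What is at stake is the precision of one estimate. Aim 1 is to characterize acute effects, and a rise in pressure is already expected. Its size, with an interval, is therefore more informative than a p-value, and the data to estimate it better are collected anyway.

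**Working it through.** **Inputs from the documents.** 90 per arm (section 3.3.12.7); pre-dose limit 140/90 (3.3.6.2, 3.3.8.1.3); mean rise of about 20 mm Hg systolic and 12 diastolic in a cited earlier study (4.1.3.1.1).

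**Inputs assumed.** In-session SD of 12-15 mm Hg, and a correlation r between pre-dose and in-session pressure of 0.3-0.6. The documents give neither. They also give no power or precision figure for blood pressure to reproduce; the stated power of 0.8 concerns drinking.

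**Step 1, ratio of standard errors.** With equal pre-dose and in-session SDs:
- covariance analysis against a t-test on in-session values: sqrt(1 - r²)
- covariance analysis against a t-test on change: sqrt(1 - r²) / sqrt(2(1 - r)) = sqrt((1 + r)/2)

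| r | against in-session t-test | against change t-test |
|---|---|---|
| 0.3 | 0.954 (5% narrower) | 0.806 (19%) |
| 0.4 | 0.917 (8%) | 0.837 (16%) |
| 0.5 | 0.866 (13%) | 0.866 (13%) |
| 0.6 | 0.800 (20%) | 0.894 (11%) |

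Allowing for the lost degree of freedom and chance imbalance changes these by less than one percentage point.

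**Step 2, in mm Hg.** At SD 15, the t-test half-width on in-session values is 1.96 × 15 × sqrt(2/90) = 4.4. At r = 0.5 the adjusted half-width is 4.4 × 0.866 = 3.8. At SD 12 the figures are 3.5 and 3.0.

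**Step 3, effect of the 140 mm Hg limit.** Let v be the variance of pre-dose systolic pressure after truncation, divided by its variance before. The residual SD stays at sqrt(1 - r²) of the untruncated in-session SD. The in-session SD becomes sqrt(r²v + 1 - r²) and the SD of change sqrt((1 - r)²v + 1 - r²). At r = 0.5 these two coincide, so the gain is the same under both readings of the plan. Assumed untruncated distributions:
- Mean 120, SD 12: v = 0.815; ratio 0.866 / sqrt(0.25 × 0.815 + 0.75) = 0.866 / 0.977 = 0.887. Gain about 11%; half-width 3.4 to 3.0 mm Hg.
- Mean 135, SD 15: v = 0.442; ratio 0.866 / sqrt(0.25 × 0.442 + 0.75) = 0.866 / 0.928 = 0.934. Gain about 7%; half-width 4.1 to 3.8 mm Hg.

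In these two cases the correlation remaining in the dosed sample is 0.46 and 0.36.

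**Step 4, validity.** In a simulation without truncation (4,000 trials at each of r = 0.3, 0.5 and 0.7), the 95% intervals from all three methods covered the true difference in 94.7-95.4% of trials.

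**Step 5, detection.** At SD 15 the unadjusted standard error is 15 × sqrt(2/90) = 2.24 mm Hg. A between-group difference of 20 mm Hg is 20/2.24 = 8.9 standard errors. The cited 20 mm Hg is a rise under psilocybin and not a contrast with diphenhydramine, but even half of it gives 10/2.24 = 4.5.

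**The case against.** The strongest reply is that this is an efficiency preference. The t-test is valid, the expected effect is several times the half-width, and the gain under the truncated scenarios is 0.3-0.4 mm Hg. The plan sets no precision target for blood pressure and presents these tests as a deliberately liberal safety screen. All of that stands, and it limits the point to an optional improvement.

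Three stronger readings are tempting, and the documents do not support them.
- A reader might infer that the plan discards the pre-dose reading. The safety measure is defined as change, and the t-test sentence follows a restatement of that definition, so the test may well be on change. The text does not settle it.
- A reader might infer that the comparison is biased, or that a rise could be missed. Steps 4 and 5 show otherwise.
- A reader might infer that baseline adjustment was considered and rejected, or is absent from the whole plan. No passage says so, and the separate SAP may contain it.

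A further objection concerns the remedy. At session 2 the same-morning reading comes after randomization and the first dose, and exists only for those who continue and meet the limit again. Adjusting for it could remove part of a treatment effect. This stands, and the fix below allows for it.

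**Conclusion.** The point holds as a free improvement. Whichever quantity the t-test is applied to, adjusting for pre-dose pressure gives an estimate at least as precise, from data that dosing already requires. With an assumed correlation of 0.3-0.6 in the dosed sample, the interval narrows by about 5-20% against in-session values and 11-19% against change. The change figures also assume equal pre-dose and in-session SDs. The dosing limit pushes the gain toward the lower part of the range: about 7-11% at an untruncated correlation of 0.5, for the systolic distributions assumed in step 3. The loss is one of precision only; the test remains valid and the conclusion that pressure rises would not change. The size rests on an SD and a correlation that the documents do not give.

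**What to change.** In section 3.3.12.2.2, replace the blood pressure t-test, for each double-blind session, with a linear model of one pre-specified in-session value (for example the peak) on treatment group, session-1 pre-dose pressure and site. Report the adjusted difference with a 95% interval. Do the same for pulse.

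- Use the session-1 value, measured before the first dose, as the covariate at both sessions. At session 2, use the same-morning value only in a sensitivity analysis.
- Site belongs in the model because randomization is stratified by site.
- Rating scales with no pre-dose value can keep the t-test.
- The value chosen depends on when readings are taken, so the differing schedules in sections 3.3.8.1.3, 3.3.10.1 and 3.3.10.9 must be reconciled.
- Check the separate SAP first. If it already specifies baseline adjustment, align section 3.3.12.2.2 with it.

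The cost is about one sentence of analysis text, with no new data and no change to conduct.

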
**Aim 1:** To characterize the acute effects of PO psilocybin 25 mg/70 kg, 30 mg/70 kg, and 40 mg/70 kg in alcohol dependent patients: Hypothesis 1: The drug will be well-tolerated, and acute effects will be similar to those observed in normal volunteers.

**Aim 2:** To evaluate the effect of psilocybin treatment on drinking outcomes for 32 weeks after the first administration, relative to diphenhydramine control. Hypothesis 2: A greater decrease in percent heavy drinking days will be observed among participants receiving psychoactive doses of psilocybin in combination with psychosocial treatment than in those receiving diphenhydramine.

**Aim 3:** To test whether or not characteristics of the drug administration session experiences mediate effects of psilocybin on short term (1 week) persisting effects and post-session drinking behavior. Hypothesis 3: Intensity of experience during the drug administration sessions will predict post-session changes in craving, self-efficacy, and motivation, and these changes will in turn predict changes in drinking behavior during the 32 weeks following initial drug administration.

**Aim 4:** To evaluate the explanatory value of changes in alcohol craving, self-efficacy, motivation, and other psychological domains in accounting for the observed experimental effect of psilocybin relative to diphenhydramine control. Hypothesis 4: Changes in craving, self-efficacy, and motivation will mediate the effects of psilocybin treatment on drinking behavior.

**Aim 5:** To evaluate pre-post changes in drinking in participants after they receive psilocybin in the third session. Hypothesis 5: participants in the control group will show decreases in drinking during the 16 weeks following the psilocybin session at week 38.

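### Leaving the adverse-event tests uncorrected does not make them sensitive: at 90 per arm they have little power for most uncommon harms, and the supplied text plans no risk difference or interval

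*Combined protocol and SAP*

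**What the plan says.** The tolerability paragraph of Section 3.3.12.2.2 (Aim 1, Method) begins "Adverse events will be tabulated". The comparison between arms is then set out in one sentence: "AEs will be MedRA coded and groups contrasted using Chi squared or Fisher's exact test". There is no rule for choosing between the two tests and no mention of a continuity correction. The paragraph closes with "All tests will be unprotected against inflated Type I error thus providing the most liberal estimate for potential safety concerns".

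Section 3.3.12.2.1 lists clinically significant AEs and serious adverse events (SAEs) among the primary safety measures. Hypothesis 1 in Section 2 predicts: "The drug will be well-tolerated, and acute effects will be similar to those observed in normal volunteers". No criterion for tolerability is attached to it.

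The only power statement, in Section 3.3.12.7, concerns percent heavy drinking days: "Power analysis is based on the primary outcome analysis contrasting the psilocybin group with the control group". No power, significance level or sidedness is stated for the AE tests. Section 3.3.12 refers the reader to a separate SAP for the full analyses; no such text was among the material supplied.

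**The concern.** A reader of the closing sentence may conclude that the AE comparison is set up to catch harm as readily as possible. Omitting a multiplicity correction keeps each test at its nominal level, but it does nothing about the chance that a real excess goes undetected. For a safety comparison that chance is the main risk, and it is largest for uncommon events. Section 4.1.3.1.1 itself acknowledges rare but potentially serious effects of psilocybin.

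The second issue is that a test result is the only between-group AE output described. Without a risk difference or interval, the report would not show how large an excess the data leave open, and Hypothesis 1 has no criterion to fill that gap.

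**Working it through.** The plan gives no figure for the AE contrasts, so there is none to reproduce.

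**Inputs**
- Arm sizes, from Section 3.3.12.7: "90 assigned to psilocybin and 90 to control". The 5% attrition there is not applied, because Section 3.3.5 times randomization "in order to restrict the intent-to-treat sample to patients who actually receive study medication".
- Two-sided 0.05 for each AE test: assumed, borrowed from the efficacy analysis.
- Event rates: assumed. The documents give no control-arm AE rates.

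**Step 1: smallest significant split against zero events**

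For *a* events v 0, the two-sided Fisher p-value is 2 × C(90, a) / C(180, a).
- a = 5: p = 0.059.
- a = 6: p = 0.029.

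Uncorrected chi-squared is X² = N(ad − bc)² / (product of the four margins).
- 5 v 0: 180 × 450² / (90 × 90 × 5 × 175) = 5.14, p = 0.023.
- 4 v 0: 180 × 360² / (90 × 90 × 4 × 176) = 4.09, p = 0.043.
- 3 v 0: p = 0.081.

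Fisher therefore needs at least 6 v 0, and chi-squared at least 4 v 0.

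**Step 2: power for 5% v 0%**

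With no control events, power is a binomial tail with n = 90 and rate 0.05.
- Fisher: P(X ≥ 6) = 0.295.
- Chi-squared: P(X ≥ 4) = 0.664.

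**Step 3: power in general**

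Power is the sum of Bin(a; 90, p1) × Bin(b; 90, p2) over all tables (a, b) with p < 0.05.

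| Psilocybin v control | Fisher | Uncorrected chi-squared |
|---|---|---|
| 2% v 0% | 1% | 11% |
| 3% v 0% | 5% | 28% |
| 5% v 0% | 29% | 66% |
| 5% v 1% | 15% | 34% |
| 10% v 5% | 17% | 24% |
| 10% v 2% | 52% | 63% |
| 15% v 5% | 55% | 63% |
| 20% v 5% | 85% | 89% |
| 30% v 10% | 91% | 93% |

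A common convention uses Fisher when an expected count is below 5 and chi-squared otherwise. It gives 29% (5% v 0%), 16% (5% v 1%), 23% (10% v 5%) and 89% (20% v 5%).

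**Step 4: actual size, same sum with equal rates**

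| True rate in both arms | Fisher | Uncorrected chi-squared |
|---|---|---|
| 1% | 0.02% | 1.1% |
| 2% | 0.3% | 3.6% |
| 5% | 1.9% | 4.2% |
| 10% | 3.0% | 5.1% |

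**Step 5: what an interval would show for 5/90 v 0/90**

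The risk difference is 5.56%. The Wilson limits are 2.40% to 12.35% for 5/90 and 0% to 4.09% for 0/90. The Newcombe limits are:
- Lower: 5.56 − √[(5.56 − 2.40)² + (4.09 − 0)²] = 0.4%.
- Upper: 5.56 + √[(12.35 − 5.56)² + 0²] = 12.4%.

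For 0/90 in one arm, the exact one-sided 95% upper limit is 1 − 0.05^(1/90) = 3.3%.

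**The case against.** **The word 'liberal' is correct as used.** The sentence ties it to the absence of Type I error protection and makes no claim about power. That stands: the sentence is open to misreading, not false.

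**The two tests should not be lumped together.** A reader might infer that both are strongly conservative here. Step 4 shows this for Fisher at low event rates. Uncorrected chi-squared is strongly conservative only near a 1% rate.

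**Not every harm is likely to be missed.** A reader might infer that the trial misses most relevant harms. The calculations do not support that. Common effects have 85% power or more at 20% v 5%. The paranoia rate quoted in Section 3.3.8.1.3 (6/36, or 16.7%, in volunteers at 0.43 mg/kg) against an assumed 5% control rate gives 67% by Fisher and 74% by chi-squared. The weakness lies with uncommon events and small differences.

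**The plan does not equate non-significance with tolerability.** A reader might infer that 'well-tolerated' will be concluded from p > 0.05. No section says so. AEs are also tabulated, Section 3.3.13 assesses tolerability after stage 1 and plans safety looks without formal testing, and Sections 4.5.3 and 4.5.4.3 provide for DSMB review, with an unblinded comparison if levels are concerning. These steps govern trial conduct, however. They do not supply an estimate or a criterion for the reported tolerability conclusion.

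**The separate SAP may already specify intervals.** That cannot be excluded. The wording in Section 3.3.12.2.2 would still merit clarification.

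**Conclusion.** The point holds in a limited form. Leaving the AE tests uncorrected is liberal about multiplicity only. At 90 per arm, power for the uncommon-event contrasts examined, with differences of 2 to 5 percentage points, runs from 1% to 34%, except for chi-squared at 5% v 0% (66%). The result can also turn on which of the two named tests is used. The supplied text specifies no between-group AE estimate or interval and no criterion for 'well-tolerated'. It therefore does not rule out reading non-significance as tolerability, but neither does it plan that reading.

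These figures rest on full arms of 90, an assumed two-sided 0.05 and assumed event rates. The conclusion about intervals is subject to what the separate SAP contains. This is a low-severity reporting improvement and does not call the design into question.

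**What to change.** In Section 3.3.12.2.2:

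1. Reword the closing sentence so that 'liberal' refers only to the absence of multiplicity adjustment.
2. For SAEs, clinically significant psychological AEs and MedDRA terms in the double-blind period, make the main summary the number of participants with the event by arm and the risk difference with a 95% score interval. Choose Newcombe or Miettinen-Nurminen in advance.
3. Where no psilocybin participant has the event, give the exact one-sided 95% upper limit for that arm (3.3% for 0/90).
4. Keep p-values as descriptive, and state that p > 0.05 is not evidence of no excess.

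This does not set a tolerability margin; it makes the excess still compatible with the data visible. It needs no new data and no design change. The cost is a few more table columns and a tolerability statement that carries visible upper bounds, and so reads less favourably.
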